## 11.4. MONITORING

The trial monitors should monitor the trial on a periodic basis to ensure that the rights and welfare of patients are safeguarded, that the protocol, applicable regulatory and ethical requirements are met, that the necessary documentation is available, and that the data collected accurately reflect the CRF data.

## 11.5. AMENDMENTS OR MODIFICATIONS TO THE PROTOCOL

Once a protocol has been approved by the CEIm and authorized by the Spanish Agency of Medicines and Health Products, neither the investigator nor the sponsor can make modifications or alterations without the written consent of both parties. If it is necessary to make a modification or alteration to the protocol, this modification should be discussed and agreed between the principal investigator and the sponsor and signed by both parties. Amendments to the protocol will form an integral part of the original protocol. Any modification in the authorized conditions for the trial that is considered relevant, because it affects the safety of the subjects, cannot be carried out without the prior favorable opinion of the IRB/IEC and the authorization of the AEMPS.

## 11.6. Publication of test results and use of the information.

The results of this clinical trial will be reported at scientific congresses and published in a scientific journal of the highest possible impact. The results of the trial and any proposal for publication will be sent to the sponsor at least 30 days prior to submission for publication.

## 11.7. Basic trial regulation.

The Principal Investigator and/or the HOSPITAL undertake not to use or transmit to third parties, nor to divulge and/or publish the results obtained in this Trial without the prior written consent of the IBSAL, the sole promoter of the trial. In any case, the following conditions must be respected:

- a) The results of the present study may not be published until the completion of the trial or earlier, if agreed by both parties.
- b) The sponsor will not cite the name of the investigators without their authorization, except in the case of references to previously published work.
- c) The sponsor will allow the publication of the data obtained in this trial in journals of recognized scientific prestige and its dissemination in seminars and conferences within the medical professional field, provided that the provisions of paragraph a) of this section are respected and that the final draft of the article is reviewed by the sponsor

within a minimum period of thirty days.

## 12. STATISTICAL ANALYSIS

The data collection notebooks will be processed by a pre-set and validated Clinical Data Computer System. After double data recording, resolution of all inconsistencies and coding using the medical dictionaries, a final quality control process will be applied and in case of compliance the database will be considered free of errors and will proceed to freeze and perform the statistical exploitation of the data. The results of the clinical trial will be analyzed in the intention-to-treat population.

### 12.1. Population for analysis

The efficacy and safety analysis will include all patients enrolled in the study. Efficacy analyses will be performed on data from the intention-to-treat population.

The term "treatment period" used for efficacy and safety analyses refers to the period from cell administration and the end-of-treatment week (+/-7 days). This period will form the basis for the efficacy and safety summaries.

The primary efficacy data set will consist of all patients in the study who have completed all treatment. Events occurring in patients who have been withdrawn early will also be included if the patients meet the withdrawal criteria.

For the primary endpoints, an analysis will be conducted using the evaluable patient data set as well as the primary efficacy data set. Summaries of the safety data will include all patients treated in the study. The primary and secondary data set will be defined in a statistical analysis plan.

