## OBJETIVES

### Main objective:

To analyze the efficacy of the application of Hemopatch® directly on the pulmonary suture line as prevention of postoperative air leak in patients at high risk after pulmonary resection. Decrease in the postoperative air leak rate (air outflow through the drains on the 5th postoperative day).

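### Section 12.1 supports two different primary analysis sets, intention-to-treat and completers plus withdrawn patients' events, and does not say which decides the trial

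*Combined protocol and SAP*

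**What the plan says.** The primary outcome is air leak on day 5, given in the main objective as "air outflow through the drains on the 5th postoperative day".

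Five statements bear on who is analysed for it:

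- Section 12: "The results of the clinical trial will be analyzed in the intention-to-treat population".
- Section 12.1, first sentence: "The efficacy and safety analysis will include all patients enrolled in the study". The next sentence repeats intention-to-treat for efficacy.
- Section 12.1, third paragraph: "The primary efficacy data set will consist of all patients in the study who have completed all treatment". It continues: "Events occurring in patients who have been withdrawn early will also be included if the patients meet the withdrawal criteria".
- Section 12.1, on the primary endpoints: "an analysis will be conducted using the evaluable patient data set as well as the primary efficacy data set". The evaluable set is not defined, and intention-to-treat is not named in this sentence.
- Section 12.1, last sentence: "The primary and secondary data set will be defined in a statistical analysis plan". The document as supplied contains no such definition.

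Section 12.2 rules out imputation of unavailable data outside the patient-reported records. Section 12.5 requires deviations from the statistical plan to be included in the final report.

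**The concern.** A completer set is not an intention-to-treat set. The section attaches the word primary to the former after committing the trial to the latter. Either could be defended once the data are known, and because the trial is open-label, treatment assignment is visible to those who judge withdrawal and compliance.

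Two features of the completer rule make the choice matter. On its plain reading, the events sentence admits a withdrawn patient who had an event and leaves out one who did not, so outcome affects membership. Also, finishing all treatment has no stated meaning in the control arm, which under section 5.2.2 receives each centre's usual preventive measures. Membership could then be decided differently in the two arms, and the comparison could be biased in either direction.

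**Working it through.** **1. Side by side.** A randomised patient who withdraws before day 5 and has no leak is in the analysis under section 12. Under the third paragraph of 12.1, read plainly, that patient is out. The two rules give different denominators for the same endpoint. The deferral to an SAP does not rank them, and section 12.5 only governs how deviations are reported.

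**2. The plan's own figure.** Inputs from section 5.2.2: 27% control, 13.5% experimental, two-sided alpha 0.05, 1:1; the stated beta of 0.80 is read as power. With mean rate 0.2025:

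n = [1.960·√(2·0.2025·0.7975) + 0.842·√(0.27·0.73 + 0.135·0.865)]² / 0.135² = (1.114 + 0.472)² / 0.018225 ≈ 138 per arm, 276 in total.

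The stated size is reproduced, so power of 0.80 belongs to all 276 patients; section 5.2.2 describes no allowance for losses. Exact binomial enumeration with the uncorrected chi-square test gives 80.4% power, and 2.5% per side when both rates are 27%.

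**3. Illustration of the two rules.** The documents give no withdrawal rate, so all of these are assumptions: no true effect (27% in both arms), control n = 138, a fraction f = 5% lost from the experimental arm only, and leak rate q among those lost.

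- Rule A, events kept and event-free withdrawn patients left out: n = 138·[1 − f(1 − q)], leak rate 0.27/[1 − f(1 − q)]. At q = 27%: 138·0.9635 ≈ 133 and 0.27/0.9635 = 28.0%.
- Rule B, non-completers dropped with their leaks: n = 138·(1 − f) ≈ 131, leak rate (0.27 − f·q)/(1 − f). At q = 60%: (0.27 − 0.03)/0.95 = 25.3%.

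| q | A: n, leak rate | A: significant against patch | B: n, leak rate | B: significant favouring patch |
|---|---|---|---|---|
| 27% | 133, 28.0% | 3.8% | 131, 27.0% | 2.5% |
| 40% | 134, 27.8% | 3.5% | 131, 26.3% | 3.3% |
| 50% | 135, 27.7% | 3.4% | 131, 25.8% | 4.1% |
| 60% | 135, 27.6% | 3.2% | 131, 25.3% | 5.1% |

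With the same loss in both arms, either rule gives about 2.5% per side. Rule B does nothing when those lost leak at the base rate of 27%; it inflates only when they leak more often and leave mainly one arm.

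**4. What intention-to-treat costs.** If a fraction f of the experimental arm is not patched and leaks at rate q, the arm's rate is either (i) f·q + (0.27 − f·q)/2, halving the leak rate in the remaining patients, or (ii) f·q + (1 − f)·0.135, fixing patched patients at 13.5%. The two agree at q = 27%.

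| f | q = 27% | q = 50%, (i) | q = 50%, (ii) |
|---|---|---|---|
| 2% | 13.8%: power 78.5% | 14.0%: 76.9% | 14.2%: 75.2% |
| 5% | 14.2%: power 75.6% | 14.8%: 71.1% | 15.3%: 66.4% |

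**The case against.** The best defence is that intention-to-treat is stated twice and all enrolled patients once, that an SAP is promised, and that the sets may hardly differ. Treatment is a single intra-operative application, follow-up is daily in hospital, and section 6.4 recommends continuing once the product has been given. This stands as a limit on size. It does not settle which rule governs, because the specific sentence on the primary endpoints names the other sets.

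The wording also has more than one reading. Events is undefined: it could mean adverse events, or any data recorded before withdrawal. If it means adverse events, the primary set is completers only, which still conflicts with intention-to-treat. If finishing treatment simply means having been patched, every patched patient stays in with or without a leak, and Rule A touches only patients who leave before or during surgery.

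A reader might infer more than the documents support:

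- *That experimental patients who fail the leak check go unpatched and vanish, with no control counterpart.* Sections 5.3 and 7.3 place application after a check for no leak or grade 1, which can be read as a sequence to be achieved before patching. No text says that a patient failing it goes unpatched. Nor is the timing of randomisation settled. Section 8.2 mentions it at the selection visit once eligibility is verified, but class D eligibility uses a score that counts adhesions seen during surgery, and section 5.3 says only that randomisation follows the order of inclusion. This is a possible route, no more.
- *That the post-operative item in section 6.3 (ventilation or reintervention) removes randomised patients.* No text says so; section 12.1 merely fails to say that it does not.
- *That the trial is biased towards the patch.* The plain reading of the events sentence works against it, and the inflation in its favour needs one-sided loss of patients who leak more than average.

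**Conclusion.** The conflict is real and the section is wrong as written: the primary analysis set is not fixed. That conclusion rests on the text alone and needs no assumed withdrawal rate.

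The numerical consequence is conditional. Under the assumed 5% one-arm loss, the one-sided error is 3.2% to 3.8% against the patch or 2.5% to 5.1% in its favour, depending on the rule and on the leak rate among those lost. With few or balanced losses it stays near the nominal 2.5%. The figures show that the choice of set can matter. They do not predict what will happen in this trial.

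**What to change.** In section 12.1:

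1. Name one primary efficacy set: all randomised patients, analysed as randomised, for air leak on day 5.
2. Delete the events sentence. Count withdrawn or untreated patients by their observed day-5 status, leak or no leak.
3. Define the completer and evaluable sets for both arms, including what completion means for a control patient, and use them only for sensitivity analyses.
4. State one rule for missing day-5 status, identical in both arms, as an explicit exception to section 12.2, with a sensitivity analysis.
5. State that the post-operative item in section 6.3 does not remove a randomised patient from the primary set.

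This is wording only, with no extra patients or visits, and should be settled before the database is frozen. The price is dilution: patients who do not receive the patch stay in the experimental arm. From a planned 80.4%, power would be about 75.2% to 78.5% if 2% are unpatched and 66.4% to 75.6% if 5% are. Those shares are assumed, and the ranges depend on the leak rate in unpatched patients and the rate assumed in patched ones. Section 12 already implies this cost by committing to intention-to-treat.

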### 12.2. Procedures for handling non-existent, unused and confusing data

All available safety and efficacy data will be included in the data lists and tables. No imputation of values will be made for unavailable data.

Potentially confusing or erroneous data will be reviewed in accordance with standard data control procedures.

Analyses of patient-reported records (PNRs) will impute missing data using the last observation carried forward. The missing pattern will be examined prior to any imputation. If the missing pattern is obviously informative, the impact of non-random missing data will be assessed using sensitivity analyses.

For RNP analyses, if one item of a subscale is missing from several subscales, the average of the remaining items will be used as the scale score, provided that at least half of the items of that scale are available.

### **12.3. Statistical methods**

Those commonly used in biomedicine (i.e., Student's t-test and Mann-Witney U test for quantitative variables and Chi-square for categorical variables; comparative analysis for paired samples will be performed by repeated measures ANOVA).

In principle, no intermediate statistical analyses will be performed.

The analysis will be performed at the University Hospital of Salamanca.

### **12.4. Safety análisis**

Safety assessments will depend on the incidence, intensity and type of adverse events as well as clinically significant changes in the patient's physical examination findings. Safety variables will be included in a table and provided for all patients.

All adverse events occurring during the study will be included in data lists organized by patient. Those events that are considered treatment-related (possibly, probably or definitely related to treatment) will also be included in a table. A table listing adverse events by maximum intensity will also be provided. Deaths, serious adverse events and adverse events involving discontinuation of treatment will also be classified in another table.

### **12.5. Procedures for reporting deviations from the original statistical plan.**

All deviations from the original statistical analysis plan are included in the final clinical study report.

## **ANNEX I: SUMMARY OF FOLLOW-UP**

A-Hospital follow-up: daily visit until hospital discharge, the duration of which depends on the clinical evolution. For this purpose, the following are taken into account:

Clinical parameters:

- The patient is capable of self-care
- Afebrile
- Does not require opioids for pain control.
- Absence of significant effusion or pneumothorax

Analytical parameters:

- Normal blood count, coagulation and biochemistry.

B-Follow-up at one month-3 months after hospital discharge: FIRST POST-OPERATIVE

VISIT IN CONSULTATION

To evaluate the clinical evolution especially related to the appearance of complications.

Data collection: special attention to the patient's clinical situation Radiological: Chest X-ray, PA and L projections.

**ANNEX II: POSTOPERATIVE PROLONGED AIR LEAK RISK SCALE**

Variables	PUNCTUATION
AGE > 65 (years)	1
BMI < 25.5 m/kg 	2
FEV 1 < 80%	1.5
Presence of pleural adhesions	1

BMI = body mass index; FEV1 = forced expiratory volume in one second;

**PAL risk scale**

Class A (punctuation 0)

Class B (punctuation 1)

Class C (punctuation 1.5–3)

Class D (punctuation > 3)

Brunelli A, Varela G, Refai M, Jiménez MF, Pompili C, Sabattini A, et al. A scoring system to predict the risk of prolonged air leak after lobectomy.

Ann Thorac Surg 2010;90:204-9

### **ANNEX III: MACCHIARINI INTRA-OPERATIVE AIR LEAK SCALE**

After performing the lung sutures, the parenchyma is immersed in saline and the lung is progressively ventilated with a pressure of 25 cm H2O.

Grade 0 no bubble output

Grade 1 a countable number of bubbles are formed

Grade 2 if there is a small stream of bubbles

Grade 3 if they are coalescing bubbles

**ANNEX IV: IDENTIFICATION OF THE PRODUCT IN RESEARCH LABELING**

HEMOPATCH hemostatic sealant ("HEMOPATCH") consists of a soft, thin, pliable and flexible patch of bovine-derived collagen coated with NHS-PEG (pentaerythritol polyethylene glycol ether tetrasuccinimidyl glutarate). The white side, which is applied to the tissue, is coated with a thin layer of NHS-PEG providing a firm adhesion to the tissue, thus sealing the bleeding surface and inducing hemostasis at the same time. Due to its flexible structure, the application of HEMOPATCH to the site where hemostasis is desired is easily controlled. The uncoated side is marked with blue squares of a biocompatible dye to differentiate it from the coated side.

For the HEMOPATCH/FAP/2014 clinical trial, HEMOPATCH 4.5 x 9 cm patches will be used. They come in boxes of 6 packs with 3 patches inside each of the packs, including each patch inside 2 envelopes: one sealed aluminum outer and a second cellulose inner, to maintain the sterility of the device.

Since the sponsor of the clinical trial is not the owner of the patent of the product under investigation, an agreement has been reached with the same (Baxter España), so that the Hemopatch® patches will be supplied by said company, at no additional cost to the study sponsor, in their usual marketing format. This means that each package (containing 3 patches) will bear the CE marking. The product under investigation is currently marketed for the indication of hemostasis control in surgical procedures, with CE marking. The reason for its experimental use in this study is its use in the indication of prevention of prolonged air leak in patients at risk, an indication not approved at present and not covered by the CE marking. This marking will be removed by the developer before supplying the product to the centers, by means of an opaque marker. Also, following the indications of RD 1591/2009 and Directive 93/42/CE, the container will be relabeled, adding an adhesive label with the study protocol code and the legend "Exclusive use for clinical research".

Once relabeled, its distribution and storage will be made directly by the sponsor to the operating room warehouse provided in each center for that purpose, accessible only to the investigators participating in the study and in boxes containing 6 Hemopatch® containers each, also labeled with the study protocol code and the legend "Exclusive use for clinical research".

## ANNEX V: DATA COLLECTION BOOKLET

### **Rules for filling in the CRD**

Each investigator agrees to:

- Register the patient as soon as the patient is included in the study.
- Fill in the data collection sheets for each patient.

For the correct completion of the sheets, the following should be taken into account:

- The sheets on which it is indicated, must be dated and signed by the authorized principal investigator.
- All the boxes must be filled in. If you do not have the requested data, you should write ND (not available).
- Unusual or extreme results, or those that do not agree with the expected sequence, should be checked. They will be corrected by initialing, signing and explaining.
- Laboratory results that exceed the normal ranges established by the center's laboratory should be checked by the investigator and their meaning should be noted next to the data, initialed and signed.
- He/she will try to write the open questions in legible handwriting, otherwise it will be considered as missing information.
- The investigator will perform a final check or review of each and every CRD.
- The data should be collected with a black ballpoint pen.
